The Asia-Pacific region has the highest incidence of HCC, with >50% of all the cases in the world ¹. In addition, >80% of HCC cases in China occur due to viral hepatitis and cirrhosis ^{11, 12}. Of note, pancytopenia is a common clinical manifestation of liver cirrhosis ^{13, 14}. Therefore, the number and frequency of peripheral blood lymphocytes in many patients with HCC are lower than in the normal population ¹⁵. Furthermore, the decline of immune system function is the basis of the occurrence, development, recurrence, and metastasis of various tumors, including the decrease in anti-tumor killing and immune monitoring functions ¹⁶. TA(C)E can induce tumor necrosis, and ischemia-reperfusion injury can induce further tumor cell damage. TA(C)E is considered to improve tumor immunogenicity by releasing antigens and stimulating cytotoxic lymphocytes (CTL) recruitment in tumors ¹⁷. After reperfusion, natural killer T (NKT) cells are activated rapidly by CD1d ¹⁸. Invariant NKT (iNKT) cells are enriched in the human liver, and they express a limited T-cell receptor (TCR) β spectrum and unique TCR α rearrangement (V α 24-J α 18 in humans and V α 14-J α 18 in mice) ¹⁹. Clinical trials have shown that activated iNKT cells can rejuvenate depleted CD8 $^{+}$ T cells and natural killer (NK) cells ²⁰⁻²⁴. Some of these trials activated iNKT with aGalcer-loaded monocytic dendritic cell vaccines and others adoptively transferred iNKT cells. These activated or reactivated lymphocytes can help remove residual cancer cells and prevent tumor recurrence and metastasis. Therefore, TA(C)E

combined with adoptive iNKT therapy might be an option for the treatment of HCC.

In our previous phase I trial ²⁵, the adoptive transfer therapy of autologous iNKT cells in patients with recurrent or refractory Barcelona Clinic Liver Cancer (BCLC) B/C liver cancer demonstrated a partial clinical response and objective immune response, with very slight side effects. Therefore, we will conduct a multicenter, randomized, open trial in BCLC B/C stage patients with HCC after failure to TACE to explore the efficacy and safety of TAE combined with adoptive autologous iNKT cell therapy compared with TAE alone.

2. Study Design and Participants

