1) the use of research drugs is not consistent with the clinical regimen, and has a significant impact on the evaluation of efficacy and safety, 2) those without any record, 3) those who did not take research drugs.

TACE Failure Criteria:

1) Intrahepatic lesion [i, two or more consecutive ineffective responses seen within the treated tumors (viable lesion >50%), even after changing the chemotherapeutic agents and/or reanalysis of the feeding artery, on response evaluation CT/MRI after 1–3 months following adequately performed selective TACE. ii, two or more consecutive progressions in the liver (including an increase in the number of tumors compared to that before the previous TACE procedure), even after changing the chemotherapeutic agents and/or reanalysis of the feeding artery, on response evaluation CT/MRI after 1–3 months following adequately performed selective TACE]. 2) Continuous elevation of tumor markers right after TACE, even though transient minor reduction is observed. 3) Appearance of vascular invasion. 4) Appearance of extrahepatic spread.

4. Endpoints and Definitions

The primary endpoint is the PFS, i.e., the time from enrollment to disease progression according to the modified RECIST (mRECIST) guideline in trial immunotherapeutics, or death from any cause, whichever occurred first. Secondary endpoints include overall survival (OS), objective response rate (ORR), disease control rate (DCR), quality of life (QoL), and safety. Patients without any post-baseline tumor assessment are considered non-responders. Objective responses

will be confirmed at least 28 days after the initial documentation of the response.

Progression-Free Survival: Time from the date of enrollment to the date of first documentation of tumor progression.

Progression was defined using Modified RECIST (mRECIST): an increase of at least 20% in the sum of the diameters of viable (enhancing) target lesions, taking as reference the smallest sum of the diameters of viable (enhancing) target lesions recorded since treatment started.

Overall survival: time from the date of enrollment to the date of death from any cause.

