Objective response rate: including complete response (CR) and partial response (PR) evaluated by imaging according to mRECIST for target lesions and assessed by MRI/CT. Complete Response (CR), disappearance of any intratumoral arterial enhancement in all target lesions. Partial Response (PR), at least a 30% decrease in the sum of diameters of viable (enhancement in the arterial phase) target lesions, taking as reference the baseline sum of the diameters of target lesions. Objective Response Rate = CR + PR.

Disease Control Rate: including complete response (CR), partial response (PR), and disease stabilization (SD), evaluated by imaging according to mRECIST for target lesions and assessed by MRI/CT. Complete Response (CR), disappearance of any intratumoral arterial enhancement in all target lesions. Partial Response (PR), at least a 30% decrease in the sum of diameters of viable (enhancement in the arterial phase) target lesions, taking as reference the baseline sum of the diameters of target

lesions. Stable disease (SD), any cases that do not qualify for either partial response or progressive disease. Disease Control Rate = CR + PR + SD.

The Quality of Life (QoL) will be assessed according to the EORTC (EORTC: the European Organization for Research and Treatment of Cancer) QLQ-C30 scale between the TAE-iNKT and TAE group. And the time to deterioration of QoL, as reported by the patient, with deterioration defined as a decrease from baseline of 10 points or more on the EORTC QLQ-C30 maintained for two consecutive assessments.

Safety and side-effect profiles will be assessed based on the nature, frequency, and severity of adverse events, according to the National Cancer Institute (NCI) Common Terminology Criteria for Adverse Events (CTCAE), version 4.0.3. Common Adverse events (AEs) occurring on or after the first treatment day through the end of this trial will be recorded according to NCI-CTCAE 4.03.

5. Drugs for research

Name of Drug

iNKT cells

Production of iNKT Cells

- 1) Isolate PBMCs by leukapheresis using a COM.TEC apheresis system and Lymphoprep density gradient medium.
- 2) Resuspend PBMCs in Corning serum-free cell medium KBM581 and stimulate with 100 ng/mL α -GalCer and 100 U/mL animal-free recombinant human

interleukin-2 for 48 hours; the rhIL-2 was replenished every other day.

3) Stimulate PBMCs with 1,000 IU/mL granulocyte-macrophage colony-stimulating factor and IL-4 for 1 week, and obtain mature, monocyte-derived DCs.

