4) Sort iNKT cells by using anti-iNKT microbeads according to the manufacturer's protocol on day 7.

5) Co-culture the sorted iNKT cells with mature DCs for 14 days, and collect cells for infusion on day 21. An aliquot of cells was used for immunophenotyping and functional testing.

6) Determine the frequency of iNKT cells in T cells by using a FACSCanto II cytometer.

7) The criteria for iNKT cell administration include a negative bacterial culture, a negative mycoplasma test result, and an endotoxin level < 0.05 units/mL.

Production Standards

Inspection item	Statutory (Pharmacopoeia) standard	Internal quality control standard
Color	---	Colorless or innocent
Character	---	Transparent suspension
Identification	Flow cytometry	Cellular immunophenotype
Rate of survival cell	≥95%	≥95%
Quantity (survival cell)	---	Day 7: $\geq 5 \times 10^7$; Day 21: $\geq 1 \times 10^8$
Microbial limit test	Aseptic, (bacteria and mold shall not be detected).	Aseptic, (bacteria and mold shall not be detected).

	Mycoplasma (not allowed to be detected). Endotoxin≤2EU/ml	Mycoplasma (not allowed to be detected). Endotoxin≤2EU/ml
Proportion	90%	90%

Dose and Administration

Intravenous infusion. From the date of cell collection, the cells will be infused on the 7th and 21st day of each month as a course of treatment for a total of three courses, the reinfusion dose is determined according to the patient's body surface area, which was about $10^8\sim10^9$ cells/ m^2 .

Drug Combination

Human IL-2 (25,000 IU/kg per day) will be administered (subcutaneous injection) once every other day for 1 week after iNKT cell infusion.

6. Interventions

The patients will be randomized 1:1 using a random number table to receive TAE treatment vs. the combination treatment of TAE and adoptive autologous iNKT cell infusion (TAE-iNKT). The patients in the TAE and TAE-iNKT groups will undergo TAE at weeks 0 and 4 after enrollment. TAE will be performed at the local hospitals.

In the TAE-iNKT group, iNKT cells will be administered at 1st, 3th, 5th, 7th, 9th, 11th weeks after enrollment. After iNKT cell infusion, a subcutaneous injection of interleukin (IL)-2 (25,000 IU/kg) will be administered once every other day for 1 week.

All target and non-target lesions will be assessed by chest, abdomen, and pelvis CT or MRI at baseline and every 4 weeks until week 16, and then every 8 weeks until

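### The only progression rule written out counts target-lesion growth alone, in conflict with the headline PFS definition and the planned imaging of non-target lesions

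*Combined protocol and SAP*

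**What the plan says.** Section 4 (Endpoints and Definitions) describes the primary endpoint twice. The headline sentence gives PFS as "the time from enrollment to disease progression according to the modified RECIST (mRECIST) guideline in trial immunotherapeutics, or death from any cause". The later entry gives it as "Time from the date of enrollment to the date of first documentation of tumor progression" and does not mention death.

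The sentence after that entry says that progression was defined by mRECIST and states one criterion: "an increase of at least 20% in the sum of the diameters of viable (enhancing) target lesions", relative to the smallest sum since treatment started. Nowhere in the document is a new lesion, non-target progression, new vascular invasion or extrahepatic spread named as a PFS event.

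The ORR and DCR entries in Section 4 each say that response is "evaluated by imaging according to mRECIST for target lesions and assessed by MRI/CT". The residual class is "Stable disease (SD), any cases that do not qualify for either partial response or progressive disease".

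Other sections point towards a wider scope:

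- Section 6 (Interventions): "All target and non-target lesions will be assessed by chest, abdomen, and pelvis CT or MRI", continuing until radiological progression.
- Section 1 (Background and Aims), on the purpose of the cell therapy: "These activated or reactivated lymphocytes can help remove residual cancer cells and prevent tumor recurrence and metastasis".
- Section 3 (Criteria), TACE Failure Criteria: repeated liver progression counts as failure, "including an increase in the number of tumors compared to that before the previous TACE procedure", as do the appearance of vascular invasion and of extrahepatic spread.
- Section 3, suspension and termination criteria: progression is judged by imRECIST, a different name from the one used for the endpoint.

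**The concern.** The written rule has no patient-level part. Disease that appears outside the measured targets has no stated place in PFS, and it cannot move a patient out of SD or PR. Section 1 gives prevention of recurrence and metastasis as part of the rationale, so the rule leaves out some of what the treatment is meant to prevent. The scans that would show it are planned, but the written rule makes no use of them.

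The practical risk is inconsistent counting. The trial is open-label at three hospitals and the plan describes no central or blinded reading. One reader could apply the target sentence and another the guideline as a whole, possibly knowing the arm. A patient with new metastases and stable targets may also leave the study for new antineoplastic therapy (a termination criterion in Section 3), and Section 7 does not say how PFS is then censored.

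**Working it through.** **1. One patient through the written rules.** Suppose that at week 8 the target sum is unchanged and there is a new lung lesion.

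- Increase of 20% or more in the target sum? No, so there is no progression event and the PFS clock runs on.
- Decrease of 30% or more? No, so not PR.
- Neither PR nor PD, so SD, and the patient counts in DCR.

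If the target sum had instead fallen by 30%, the same patient would be PR and would count in ORR. Under the headline sentence the outcome depends on the cited guideline, whose content cannot be checked from the documents.

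**2. Direction for PFS and DCR (no assumptions).** Let T be the time to target growth, O the time to progression elsewhere and D the time to death. Full-rule PFS is min(T, O, D) and target-only PFS is min(T, D). The first can never exceed the second, so the target-only rule gives PFS that is the same or longer in every patient. In the same way, its DCR is the same or higher.

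**3. Illustrative size.** Inputs from Section 7: median PFS 1.5 and 4.5 months, 60 patients, 20% drop-out. The plan's own hazard ratio is reproduced: 1.5/4.5 = 0.333, stated as 0.33. Evaluable patients: 60 × 0.80 = 48.

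Assumptions, none from the documents: independent exponential routes; a share q of the progression hazard lies outside the targets; no deaths; 1.5 months is the all-route control median; iNKT acts equally on both routes; each evaluable patient is followed for 6 months.

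Target-only medians are 1.5/(1−q) and 4.5/(1−q). Expected events at 6 months are 48 × the average over arms of 1 − 2^(−6/median).

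| q | TAE median (months) | TAE-iNKT median (months) | Events among 48 at 6 months |
|---|---|---|---|
| 0 | 1.5 | 4.5 | 37.0 |
| 20% | 1.5/0.8 = 1.88 | 4.5/0.8 = 5.63 | 33.9 |
| 40% | 1.5/0.6 = 2.50 | 4.5/0.6 = 7.50 | 29.7 |
| 50% | 1.5/0.5 = 3.00 | 4.5/0.5 = 9.00 | 26.9 |

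If deaths count, as in the headline definition, the lengthening is smaller.

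**4. Effect on the hazard ratio.** A target-only rule shows HR_T. The all-route value is (1−q) × HR_T + q × HR_O, where HR_O is the hazard ratio outside the targets. The route hazard ratios below are assumed.

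| Where iNKT acts | HR_T (shown) | HR_O | All-route, q = 20% | All-route, q = 50% |
|---|---|---|---|---|
| Equally on both | 0.33 | 0.33 | 0.33 | 0.33 |
| Targets only | 0.33 | 1.00 | 0.8×0.333 + 0.2×1 = 0.47 | 0.5×0.333 + 0.5×1 = 0.67 |
| More strongly outside targets | 0.50 | 0.33 | 0.8×0.50 + 0.2×0.333 = 0.47 | 0.5×0.50 + 0.5×0.333 = 0.42 |

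Against the all-route value, the target-only rule leaves the benefit unchanged in the first row, overstates it in the second and understates it in the third.

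**The case against.** The best defence is that the headline sentence governs. It cites a whole guideline, so the target sentence may be only an extract, and assessing non-target lesions until radiological progression makes little sense if only target sums count. This stands in part: the text contradicts itself and does not clearly exclude these events. It does not close the gap. The target sentence is presented as the definition, the same scope is repeated for ORR and DCR, and the criteria set is itself unsettled between Sections 3 and 4.

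The TACE failure comparison is also limited. Those are entry criteria, and liver progression there must occur at least twice in succession. They show what the protocol regards as progression, but they are not an endpoint rule.

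Three stronger readings are tempting and not supported:

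- A reader might infer that the endpoint omits the effect under test. Section 1 also gives removal of residual cancer cells as an aim, and viable regrowth in a target lesion counts as progression. Both arms receive TAE, so a randomized difference in target progression still reflects iNKT.
- A reader might infer a bias against iNKT. The direction depends on where it acts, which the documents do not show.
- A reader might take the recurrence rates in Section 1 (37% at 6 months, 61% at 12) as the missed share. They concern intrahepatic recurrence after TA(C)E, are not split between target and new lesions, and are not stated to come from TACE-refractory patients.

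**Conclusion.** The point holds as a gap and an internal contradiction in the definition of the primary endpoint, and it should be resolved before progression is assessed. What would be missed is recurrence or spread outside the target lesions. Target regrowth still counts, and death counts under the headline definition but is absent from the second one.

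Confidence is high on the omission and on the direction for PFS and DCR, which needs no assumption. The size is not known. The control medians of 1.9 to 3.0 months rest on an assumed 20% to 50% share, exponential routes, no deaths, and 1.5 months being an all-route figure, for which Section 7 gives no source. The direction of any bias in the hazard ratio is not established.

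**What to change.** In Section 4, replace the progression sentence with one patient-level definition and use it for PFS, ORR and DCR. Progression is the first of:

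- an increase of 20% or more in the viable target sum over the smallest recorded sum, baseline included;
- unequivocal progression of non-target lesions;
- any new lesion, whether intrahepatic, vascular or extrahepatic.

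Delete the restriction to target lesions from ORR and DCR, and classify CR, PR and SD by overall response. State death from any cause as an event in both PFS definitions. Name one criteria set for the endpoint, check the new wording against it, and reconcile the mRECIST wording in Section 4 with the imRECIST wording in Section 3. How treatment stopping should be decided is outside this point.

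The cost is redrafting in Section 4 and recording of new and non-target lesions. The case report form is not in the documents, so whether it already has a place for them is unknown. The imaging is already planned in Section 6. The downside is somewhat shorter PFS and lower DCR in both arms.

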This randomized, multicenter, open-labeled phase II trial will be conducted at Beijing YouAn Hospital of Capital Medical University, Beijing Shijitan Hospital of Capital Medical University, and Beijing Ditan Hospital of Capital Medical University between March 2018 and March 2020. This study will be performed according to the guidelines of the Helsinki Declaration.

3. Criteria

Inclusion Criteria:

1) 18-80 years of age, 2) TACE failure/refractory BCLC B HCC confirmed by CT, MRI, and/or histopathology, 3) life expectancy of at least 12 weeks, 4) Child-Pugh A/B, 5) adequate hematological and renal functions, including white blood cell (WBC) count $>3.0 \times 10^9/L$, lymphocyte count $>0.8 \times 10^9/L$, platelet count $>50 \times 10^9/L$, hemoglobin concentration $>85 \text{ g/L}$, and serum creatinine

concentration of <1.5-times the upper limit of normal value (ULN), and 6) previous treatment terminated at least 4 weeks before entry to this study.

Exclusion Criteria:

1) Known history of the human immunodeficiency virus (HIV) or syphilis infection, 2) clinically serious infections, 3) history of stem cell transplant or organ allograft, 4) history of severe hypertension or cardiac disease, 5) known central nervous system (CNS) tumor, 6) autoimmune disease requiring systemic therapy with immunosuppressive agents, 7) history of allergy to immunotherapy or related drugs, 8) pregnancy or lactation, or 9) deemed not suitable for cellular immunotherapy by the investigators.

Research Suspension / Termination Criteria:

1) the patient withdrew his informed consent and asked to withdraw, 2) CT/MRI examination confirmed the occurrence of PD, according to the imRECIST, 3) unable to tolerate AEs, or serious adverse events (SAE), abnormal laboratory tests or concurrent diseases, etc, and the researchers judged that it is not in the best interests of patients to continue to participate in the study, 4) the study and treatment of patients was significantly delayed for any reason, which exceeded the scheduled treatment time \geq 8 weeks from the time of the last administration, 5) other situations in which the researchers believe that it is necessary to stop treatment, 6) pregnancy occurred in the patient, 7) use new antineoplastic therapy, 8) the sponsor terminates the study.

Elimination Criteria:

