radiological progression. At the same time points, routine blood tests, tumor biomarkers, α -fetoprotein (AFP), and quality of life (QoL) will be measured.

After the end of treatment, the survival follow-up of the subjects will continue to be conducted every 3 months, while those who end treatment for reasons other than disease progression will undergo regular tumor imaging evaluation as much as possible after treatment, and survival follow-up must be carried out.

The details of follow-up are shown in the table below:

Project / time	Screening/ baseline period (-14d~0w)	The first cycle 3W \pm 7d	The second cycle 6w \pm 7d	Odd cycle \pm 7d	Even cycle \pm 7d	Out-of- group follow-up \pm 7d
Sign the informed consent form	×					
Medical history	×					
Inclusion / exclusion criteria	×					
Physical examination and vital signs	×	×	×	×	×	×
Blood routine	×	×	×	×	×	×
Urine routine	×	×	×	×	×	×
Biochemistry (liver and kidney function, blood glucose, blood lipid)	×	×	×	×	×	×
Myocardial enzyme	×	×	×	×	×	×
Thyroid function	×	×	×	×	×	×
Five items of hepatitis B	×					
Hepatitis C antibody	×					
HBV-DNA/HCV RNA quantification	×		×		×	×
Syphilis antibody	×					
HIV antibody	×					
Digestive tumor markers, AFP	×	×	×	×	×	×
Coagulation	×	×	×	×	×	×

Autoantibody	×					
T cell subsets	×	×	×	×	×	×
Detection of cell suspension (bacteria, fungi, endotoxin)	×	×	×	×	×	
Electrocardiogram	×		×		×	×
Colour Sonography	×					×
Liver enhanced MR or CT	×		×		×	×
Imaging data of other organs	×		×		×	×
Pathological examination of tumor	×					
Drug combination	×	×	×	×	×	×
Adverse events	×	×	×	×	×	×

The Implementation of TAE

- 1) Select catheterization of the feeding artery by using a microcatheter.
- 2) Perform abdominal and hepatic arteriography.
- 3) Embolization with Gelfoam until near stasis of the arterial flow.
- 4) Determine the dose of iodized oil by the tumor size or based on whether the portal vein had a tumor thrombosis.
- 5) Inject the emulsion of iodized oil until the accumulation of the emulsion in the tumor and the visualization of the portal vein branches near the tumor. (If there was a significant arteriportal shunt, embolization with Gelfoam was first performed to occlude the shunt, after which the iodized oil emulsion was infused, and embolization with Gelfoam was performed.)

7. Statistical Analysis

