The trial was designed to use a 2-sided 5% type I error and had 80% power to detect an improvement in PFS from 1.5 months in the TAE group to 4.5 months in the TAE-iNKT group, corresponding to a hazard ratio (HR) of 0.33 in terms of median PFS. In consideration of these assumptions, the trial design was powered for 60 patients to be randomly assigned in each group as the intention-to-treat population (allocation ratio of 1:1, n=30 patients in each group), and allowing for a drop-out rate of 20%. Sample size estimation was performed using PASS 11.

Continuous variables will be expressed as the median and IQR, and will be compared using t tests or Mann-Whitney tests. Categorical variables will be presented as the frequency and percentage, and will be compared using Fisher's exact tests. Survival and time to QoL deterioration will be estimated using the Kaplan-Meier method, and their 95% CIs will be calculated using the Brookmeyer and Crowley method. Survival differences will be compared using log-rank tests. Peripheral blood cells will be analyzed using Sidak's multiple comparison test. The overall two-sided significance level of $P < .05$ will be split into a two-sided significance level of $P < .01$ for tests of PFS, OS, ORR, DCR, and QoL according to the Bonferroni method (dividing the available total α (typically 0.05) equally among the chosen endpoints). If the PFS and/or all secondary endpoints are statistically significant at a two-sided significance level of 0.01, the curative effect of TAE-iNKT will be deemed better than that of TAE alone. All statistical analyses will be conducted using SAS software version 9.4 (SAS Institute).

8. Data Management.

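### QoL forms stop at radiological progression, but deterioration needs two consecutive forms, so a fall first seen at progression cannot count, and the loss is unequal between arms

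*Combined protocol and SAP*

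**What the plan says.** All references are to the combined protocol and SAP.

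- **Event definition (Section 4, Endpoints and Definitions).** Time to deterioration uses "deterioration defined as a decrease from baseline of 10 points or more on the EORTC QLQ-C30 maintained for two consecutive assessments". The same paragraph also describes a general comparison of QLQ-C30 between the arms. No QLQ-C30 scale is named.
- **Schedule (Section 6, Interventions).** Lesions are imaged "at baseline and every 4 weeks until week 16, and then every 8 weeks until" the event named at the start of the next quote: "radiological progression. At the same time points, routine blood tests, tumor biomarkers", AFP and QoL are measured.
- **End of participation (Section 3, Research Suspension / Termination Criteria).** One criterion is "CT/MRI examination confirmed the occurrence of PD, according to the imRECIST".
- **After treatment (Section 6).** "the survival follow-up of the subjects will continue to be conducted every 3 months". Further imaging is described only for patients who stop for reasons other than progression. QoL is not mentioned, and the visit table has no QoL row.
- **Analysis (Section 7, Statistical Analysis).** "Survival and time to QoL deterioration will be estimated using the Kaplan-Meier method". QoL is one of five endpoints tested at two-sided 0.01. The section gives no censoring rule for this endpoint and does not say how progression, death or an unconfirmed last fall is handled.

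**The concern.** The schedule and the event definition work against each other. The last QoL form is the one completed at the visit where progression is found. A fall of 10 points or more that first appears there has no second form to confirm it, so it does not count. Progression is a time when QoL can be expected to fall, and under the design assumptions the TAE arm reaches it sooner. Events would then be lost from both arms, and more of them from TAE. TAE-iNKT patients stay under observation longer, so more of their falls can be confirmed.

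QoL holds a 0.01 share of alpha and belongs to the success route that requires all secondary endpoints. A biased estimate, or a test with little power, would matter for that route and for any QoL statement in the report.

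**Working it through.** **Inputs from the plan.** Median PFS 1.5 months (TAE) and 4.5 months (TAE-iNKT); 30 patients per arm; QoL test level 0.01; forms at weeks 4, 8, 12 and 16, then every 8 weeks, ending at the visit where progression is found. The plan's hazard ratio reproduces: 1.5/4.5 = 0.33. It states no figure for QoL.

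**Assumptions not in the documents.** Exponential PFS, censoring at the last form, and the rates and timing of deterioration given below.

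**Step 1. Patients who can never be events.** The medians are 6.52 and 19.57 weeks. A patient who progresses by week 4 has one post-baseline form, and an event needs two.

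- TAE: 1 − 0.5^(4/6.52) = 34.6%, about 10.4 of 30.
- TAE-iNKT: 1 − 0.5^(4/19.57) = 13.2%, about 4.0 of 30.
- By week 8 the figures are 57.3% and 24.7%. Patients who progress between weeks 4 and 8 can be events only if the fall is already present at week 4.

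**Step 2. Hand check of the direction.** Suppose falls unrelated to progression occur at the same rate in both arms. A fall first seen at a 4-weekly visit is confirmed only if progression is not found at that visit. That probability is 1 − 0.346 = 0.654 for TAE and 1 − 0.132 = 0.868 for TAE-iNKT. The ratio is 0.868/0.654 = 1.33, so equal true rates appear as an excess in TAE-iNKT.

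**Step 3. Sensitivity to timing.** Simulation of 200,000 patients per arm, with background deterioration of 0.05 to 0.10 per month and 50 to 80% of patients deteriorating around progression. *Registered* is the share of true deteriorations by week 24 that count as events. HR is TAE-iNKT over TAE.

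| Progression-related fall starts | Registered, TAE | Registered, TAE-iNKT | HR as written |
|---|---|---|---|
| at progression | 9–19% | 26–46% | 1.38–1.42 |
| 1 week before | 24–29% | 39–53% | 0.81–1.06 |
| 2 weeks before | 36–40% | 51–60% | 0.67–0.91 |
| 4 weeks before | 52–59% | 71–76% | 0.57–0.78 |

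With onset at progression, about 2 to 4 events register in 30 TAE patients and 7 to 11 in 30 TAE-iNKT patients. If collection continues after progression, the HR is 0.71–0.87. A variant of the model gave 0.50–0.76 as written with onset four weeks before, and 0.60–0.84 with continued collection at every onset tried.

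**Step 4. Trials of 30 per arm, log-rank at 0.01.** Here every patient deteriorates around progression, and background deterioration is equal in both arms with a median of 26 or 13 weeks (shown in that order). Continued collection follows the same visit grid.

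| Fall starts | Median HR as written | Trials with HR > 1 | Power as written | Power, collection continued |
|---|---|---|---|---|
| at progression | 1.44 / 1.44 | 74% / 78% | about 0% | 58% / 33% |
| 2 weeks before | 0.72 / 0.86 | 22% / 36% | 5% / 1% | 64% / 40% |
| 4 weeks before | 0.51 / 0.61 | 5% / 12% | 18% / 8% | 66% / 45% |

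With onset at progression, a significant result against TAE-iNKT occurs in 1 to 3% of trials. Power is lost at every timing in the table.

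**The case against.** - **The censoring is supplied by the reader.** This stands. One might infer that the plan itself censors these patients, but Section 7 states no rule. Censoring at the last form is only the ordinary consequence of a Kaplan-Meier analysis when nothing else is specified.
- **The reversal is a corner case.** This largely stands. One might infer that most progression-related deterioration is lost and that the comparison points the wrong way. Both need onset at or very near progression. In the Step 3 model the range already straddles 1 with onset one week earlier, and with onset four weeks earlier the direction is right and more than half of deteriorations register in each arm. The documents give no timing. The unequal loss remains at every timing tried.
- **The consequence is limited.** This stands in part. QoL enters the success rule only through the route needing all secondary endpoints, and PFS alone can meet the rule. A reversal would also work against TAE-iNKT, so it would not create a false claim of benefit. The difference in loss assumes that the design medians are true.
- **Softer readings exist.** The progression limit might apply only to the 8-weekly phase, so that everyone is assessed to week 16. With onset at progression that gives an HR of 0.30–0.54 in the Step 4 model. Alternatively, the out-of-group visit, where the table ticks imaging, might carry a QoL form, which gives 0.28–0.47. Neither is written for QoL.
- **The visit grid is itself uncertain.** The Section 6 table puts imaging on even cycles, 6 weeks apart. On that grid 47% of TAE and 19% of TAE-iNKT patients progress by the first on-study form. The termination criterion uses imRECIST and PFS uses mRECIST. These passages need reconciling, but they do not remove the problem.

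**Conclusion.** The point holds. From the text alone, a fall first seen at the progression visit cannot become an event, because no later form is scheduled. Under the plan's medians, exponential PFS and censoring at the last form, the loss is informative and falls more heavily on TAE: 35% against 13% are excluded from being events by week 4.

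The size and direction of the bias in the hazard ratio are not determined by the documents. The HR is about 1.4 with onset at progression, about 0.8 to 1.1 with onset one week before, and about 0.5 to 0.8 with onset four weeks before. In the last case the direction is right, but the Step 3 estimate is still more favourable to TAE-iNKT than the 0.71–0.87 from continued collection. The likelier harm is lost events, lost power and a misleading estimate. The documents do not support a claim that the comparison will be reversed, still less significantly so.

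The primary endpoint is unaffected. The change should be made because QoL carries formal alpha.

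**What to change.** 1. **Main change.** Continue the QLQ-C30 after progression, in both arms, at the 3-monthly survival contacts already planned. State in Section 6 that QoL does not stop at radiological progression, and word Section 3 so that the termination criterion does not close questionnaire collection. Assuming no deaths or missing forms, this largely removes the dependence on timing: with 3-monthly contacts the Step 3 model gives an HR of about 0.7 to 0.9 at every onset tried, and the variant gives 0.60–0.84. The cost is one questionnaire at existing contacts, more missing forms after progression, and confirmation up to three months later, with some patients dying first.
2. **Sensitivity analysis only.** Count an unconfirmed fall at the last available form, explicitly including the progression-visit form. As the main rule it would overstate benefit for TAE-iNKT: with onset at progression, HR 0.49–0.62 against 0.71–0.87 with continued collection (variant: 0.37–0.53 against 0.60–0.84). It would also rest on unconfirmed patient reports in an open-label trial. If the progression-visit form were excluded, the HR would stay at about 1.4 and nothing would be repaired.
3. **Wording in Sections 4 and 7.** State how death and an unconfirmed last fall are handled and when patients are censored. Name the one QLQ-C30 scale and the one test that use the 0.01 share. Add a QoL row to the visit table, and reconcile the table's imaging grid with the text. This costs only drafting time.
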